To account for differences in the frequency of participant contact between the two study groups, blinded measurement staff will systematically assess for AEs in both the intervention and control groups through use of a standardized questionnaire (see MOP) that is administered at each major assessment time point. If any items are endorsed on the questionnaire, the blinded measurement staff will gather additional information and, if necessary, follow the steps for recording and reporting adverse events outlined below and in section **IX.E**. AEs uncovered in the course of treatment will also be subject to the procedures below. Combining between visit and at visit AEs will result in an alternative count that the DSMB requested. This alternative count will be comprised of all AEs, whether reported at or between visits. Blinded coaches will be unaware if an AE was reported between visits, and any duplicates will be removed by an unblinded reviewer (*DSMB Approval, 12.16.2020*)

All AEs, including those not meeting the criteria for SAEs, will be captured on an Adverse Event Form or Serious Adverse Event Form (see **Appendix D**), which must be approved of and signed by the clinical site PI. Information to be collected includes event description, time of onset (and offset if applicable), assessment of severity, relationship to study treatment, expectedness, actions taken,

and outcome of the event. Additionally, all SAEs will require categorization (e.g., death, hospitalization, permanent impairment, etc.) and documentation of any interventions implemented in response to the event.

All AEs occurring during a participant's study participation must be documented appropriately regardless of relationship. All AEs will be followed by the DSMB to adequate resolution and will be recorded in the data collection system. Any medical condition that is present at the time that the participant is screened will be considered as baseline and not reported as an AE. However, if the study participant's condition deteriorates at any time during the study, it will be recorded as an AE. Changes in the severity of an AE will be documented to allow for an assessment of the duration of the event at each level of severity. AEs characterized as intermittent require documentation of onset and duration of each episode.

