In addition to the existing procedures referenced above, the SMC recommends that as soon as child mental health SAEs are reported, to a coach or a PLAN staff designee verbally informs the participants' primary care provider and/or pediatric office staff designee with the description of the SAE, date, and referral so that they may follow-up according to their office procedure. Specifically, if a child enrolled in the study reports self-injury, a suicide attempt, or harm to others, then this will be addressed as a SAE and reported verbally to the pediatrician. The event will be reported by the individual with the most amount of information within 24 business hours of learning about the event. If a medical, behavioral, or mental health intervention is **deemed necessary to address this event, it is the pediatrician's responsibility to follow up with their patient to ensure appropriate care is provided**. Before this procedure goes into effect, the PLAN coach will communicate this plan with each pediatric practice to develop a practice-specific protocol with who to contact and how. In the event that a coach is unsure about the severity of the child mental health AE, they will collaborate with the local-site PI to determine the severity of the event and whether or not it should be reported to the pediatric office. All other mental health AEs will not be reported to the pediatrician, but will be reported to the IRB and DSMB as part of normal reporting procedures (***DSMB approved protocol addenda, 11.18.19***).

If a parent becomes pregnant, the PLAN coach will notify the clinical site PI and all weight loss treatments will be stopped. The family's continuation in the study will be limited to the child, siblings and non-participating parent if enrolled. The DCC, DSMB, and IRBs will be notified through

AE reports and a standard form for excluding participants from further data collection and treatment. Please see **Table 10** below for further details regarding AE reporting.

TABLE 10. Adverse Event Reporting Guidelines

What Event is Reported	When is Event Reported	By Whom	To Whom
Fatal or life-threatening unexpected, suspected serious adverse event	Immediately upon initial receipt of information	Contact PI	
 • IRB of Record • NHLBI • SMC • DCC • All PIs and Co-Is
		Clinical Site PIs	
 • Internal IRBs

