The primary analysis will be an intention-to-treat analysis of the child that includes all subjects. Recalling that the primary analysis involves an analysis of covariance with the 24-month value of percent over BMI (the primary outcome measure) as the dependent variable, the inclusion of all subjects will reflect the following three considerations.

1. If the 24-month value of the primary outcome is available, the child will be included in the primary analysis without the need for further considerations.
2. If the 24-month value of height and/or weight (the defining components of the primary outcome) is missing and the child had height and weight data collected by his or her pediatrician at a clinic visit that occurred within 30 days of the targeted 24-month PLAN assessment, the following considerations will be used in imputing the 24-month value to be used in the primary analysis. Those considerations are designed to account for the anticipated imprecision of values measured at the pediatrician's office.
 - a. Within each clinic, a regression model that will allow us to impute 24-month values will be generated. Using all PLAN children who attend a particular clinic and who have both precisely measured PLAN height and weight data and less precise height and weight data measured at the clinic within 30 days of the PLAN measurement, clinic-specific regression models will separately predict the true height and weight using the age and sex of the subject as well as the height and weight value measured at the clinic. The goal will be to perform these calculations on a clinic-specific basis because the causes and magnitude of measurement error may differ

from clinic to clinic. However, if the number of subjects at a clinic who have the requisite height and weight data is less than 15 (less than 5 times the number of predictors), we will use all data from all clinics at the relevant study site to perform the desired imputation.

- b. Recalling that the children of interest in this scenario have clinic data collected within 30 days of the targeted 24-month PLAN assessment, the clinic-specific height and weight value calculated above will be used to impute the PLAN 24 month values from the contemporaneous value measured at the clinic. This imputed value will be used in the primary analysis.

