The goal of secondary aim 1 is to compare the effectiveness of the FBT group with that of the UC group in the participating parent. The primary outcome variable in the parent is BMI. Since BMI is a continuous variable measured at the same time points as was the case with the participating child, the data analytic strategy for this secondary analysis is identical to what was described for the child.

C. Analysis of Secondary Aim 2 (DSMB approved protocol addenda, 11.2.18).

The goal of this aim is to determine if the weight loss impacts of FBT extend beyond the participating child by assessing the intervention in overweight/obese siblings. We hypothesize that FBT will be superior to UC for weight-eligible siblings. Analytic strategies will be similar to those used in the primary aim, the key difference being that while prior data⁷⁴ support our hypothesis of FBT benefits for siblings, power for this aim may be limited. The most important reason for this is that we have chosen not to require that participating children have a weight-eligible sibling because of the recruitment challenge such a requirement would pose. Prior data from the NHLBI-funded COMPASS study we coordinated at Washington University indicate that among 377 screened families with a participating child, 163 (43.2%) had at least one age (age 2-18) and weight-eligible sibling. Based on these numbers, we expect that there will be about 228 (= 43.2% of 528) participating families with at least one eligible sibling, with the actual number recruited being somewhat smaller because some siblings will choose not to participate.

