1. Strongly Agree
2. Agree
3. Neither Agree or Disagree
4. Disagree
5. Strongly Disagree

The content of FBT is clear.

1. Strongly Agree
2. Agree
3. Neither Agree or Disagree

4. Disagree
5. Strongly Disagree

FBT can be implemented without requiring an extensive training.

1. Strongly Agree
2. Agree
3. Neither Agree or Disagree
4. Disagree
5. Strongly Disagree

FBT can be adapted or modified to suit the needs of the interventionist.

1. Strongly Agree
2. Agree
3. Neither Agree or Disagree
4. Disagree
5. Strongly Disagree

The benefits of using FBT with my clients are obvious/visible.

1. Strongly Agree
2. Agree
3. Neither Agree or Disagree
4. Disagree
5. Strongly Disagree

The evidence regarding the impact of FBT is available.

1. Strongly Agree
2. Agree
3. Neither Agree or Disagree
4. Disagree
5. Strongly Disagree

The content of FBT is relevant to my work as a clinical treatment provider.

1. Strongly Agree
2. Agree
3. Neither Agree or Disagree
4. Disagree
5. Strongly Disagree

Coach consent

Please upload the .pdf file of the signed Coach consent.

Indicate yes or no that Coach consent is uploaded.

[figure not shown]
- No

- Yes

Why is the coach consent not uploaded? _____

D. Additional Forms

Figure 1. Study Flow Chart

PLAN Adverse Event Questionnaire

During the time since your last visit on (*insert date of last major assessment*), have you or your child:

1. Been hospitalized overnight?

YES NO

2. Been to the emergency room or an urgent care clinic?

YES NO

3. Been treated by a medical provider for illness or injury?

YES NO

4. Had any injuries (e.g., sprained ankle or broken bone)?

YES NO

5. Started any new medications or receive a change in dosage of a current medication?

YES NO

6. Experience increased symptoms of a current illness or injury (If applicable)?

YES NO

7. Seen a new counselor, psychologist, or psychiatrist?

YES NO

8. Gone long periods (8 waking hours or more) without eating to control your weight?

YES NO

9. Felt like you have lost control over your eating?

YES NO

10. Thrown up after eating?

YES NO

11. Taken laxatives or diet pills?

YES NO

12. Felt particularly nervous, worried, or anxious?

YES NO

13. Felt very sad or down? Or lost interest in things that you normally enjoy doing?

YES NO

(This change was made on 5.23.18 prior to review and approval by the DSMB, DSMB approved protocol addenda on 11.2.18)

ADVERSE EVENT FORM

The Effectiveness of Family-based Weight Loss Treatment Implemented in Primary Care

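### The pregnancy rule ends a parent's data collection as well as treatment, which creates avoidable missing 24-month BMI in Secondary Aim 1 and a risk of unequal removal between arms

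*Combined protocol and SAP*

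**What the plan says.** The rule stands in the protocol under Adverse Event Reporting Procedures: "If a parent becomes pregnant, the PLAN coach will notify the clinical site PI and all weight loss treatments will be stopped". After that only the other enrolled relatives carry on, since "continuation in the study will be limited to the child, siblings and non-participating parent if enrolled", and the oversight bodies are told through adverse event reports and "a standard form for excluding participants from further data collection and treatment". No arm is named, and nothing provides for the parent's return to assessments after delivery.

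For Secondary Aim 1 the Statistical Considerations section says: "The primary outcome variable in the parent is BMI", and "the data analytic strategy for this secondary analysis is identical to what was described for the child". The child strategy is set out under Implementation of the Intention-to-Treat Principle: "The primary analysis will be an intention-to-treat analysis of the child that includes all subjects". A missing 24-month value with no usable clinic record is multiply imputed from baseline data and any 6-, 12- and 18-month study measurements. The Missing Data section adds that people who leave early will be encouraged to keep giving follow-up measurements, above all the 24-month one. None of these sections mentions pregnancy.

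On finding events, Adverse Event Assessment and Tracking says: "To account for differences in the frequency of participant contact between the two study groups, blinded measurement staff will systematically assess for AEs", using one questionnaire in both arms. That questionnaire (Appendix D) has 13 items, and three COVID-19 items were added later. None asks about pregnancy. The nearest are an overnight hospital stay, care from a medical provider, and "Started any new medications or receive a change in dosage of a current medication".

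**The concern.** Two separate things are at stake.

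First, the rule turns a clinical event into missing outcome data. A parent who conceives early and delivers well before month 24 could give a usable 24-month BMI, but the rule ends her measurements. This holds in either arm and at any pregnancy rate. It runs against the plan's own aim of keeping 24-month data from everyone randomized.

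Second, the rule can only act on a pregnancy that staff know about, and the chance of knowing differs by arm. If more pregnant parents are removed in FBT than in UC, pregnancy-raised weights stay in the UC mean while the FBT values are replaced by imputations from earlier visits. Secondary Aim 1 would then lean toward FBT for a reason unrelated to treatment. With no pre-stated rule for such measurements, their handling would also be decided after data are in hand.

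**Working it through.** **Contacts.** Both arms have four post-baseline assessments (6, 12, 18 and 24 months). Table 6 adds coach sessions in FBT only, and its totals reproduce: 8+8+6+4 = 26 (minimum), 24+12+12 = 48 (moderate), 48+24 = 72 (maximum shown). Its note allows about 96 if sessions stay weekly. FBT parents therefore have 30 to about 100 scheduled contacts against 4 in UC. Each FBT session also begins with a weighing.

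**Timing.** Adverse Event Reporting Procedures places the questionnaire after measurement, so a UC pregnancy first mentioned at month 24 comes after the weight is recorded. The remote assessment protocol in Appendix C instead completes the survey on the scheduling call. In neither case does a rule say whether the weight counts.

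**Size.** The documents give no pregnancy rate, parent BMI standard deviation or parent effect size, so every input below except the sample size is an assumption. Let q be the share of parents whose 24-month BMI is raised by pregnancy (same in both arms), g the excess, and dF and dU the probabilities that such a parent is removed before the 24-month weight in FBT and UC. If imputed values carry no pregnancy excess, FBT keeps q·g·(1 − dF) and UC keeps q·g·(1 − dU), so

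bias toward FBT = q × g × (dF − dU).

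With 528 families allocated 50/50 there are 264 parents per arm, and 264/12 coaches = 22 per coach. For an assumed SD of BMI change of 3 kg/m² and ICC 0.04 in FBT,

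SE = 3 × √[(1 + 21 × 0.04)/264 + 1/264] = 3 × √(2.84/264) = 0.31 kg/m².

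Taking dF = 1:

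| q | g (kg/m²) | dU | bias (kg/m²) | bias/SE | two-sided type I error |
|---|---|---|---|---|---|
| 0.5% | 1 | 0 | 0.005 | 0.02 | 0.050 |
| 1% | 2 | 0 | 0.02 | 0.06 | 0.0505 |
| 2% | 4 | 0 | 0.08 | 0.26 | 0.058 |
| 4% | 4 | 0 | 0.16 | 0.51 | 0.081 |
| 4% | 4 | 0.5 | 0.08 | 0.26 | 0.058 |
| any | any | 1 | 0 | 0 | 0.050 |

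For SD 2 to 4 and ICC 0 to 0.04, the SE runs from 0.174 to 0.415. The most extreme bias is then between 0.16/0.415 = 0.39 and 0.16/0.174 = 0.92 SE.

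**Check by simulation.** A null-effect analysis of covariance was simulated with 264 per arm, 4,000 replicates and no coach clustering. Removed parents were imputed by regression on baseline and 18-month BMI. The Monte Carlo SE is about 0.004.

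| q, g, dU | simulated FBT − UC | formula |
|---|---|---|
| 1%, 2, 0 | −0.019 | −0.02 |
| 2%, 3, 0 | −0.055 | −0.06 |
| 2%, 3, 0.5 | −0.025 | −0.03 |
| 4%, 4, 0 | −0.171 | −0.16 |
| 2%, 3, 1 | −0.005 | 0 |

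The simulation agrees with the formula, and equal detection removes the bias.

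Parents who delivered long before month 24 are not in this figure. For them g may be near zero, so removal costs information more than it shifts the comparison.

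**The case against.** A reader might infer that the rule works only in FBT, so that a difference between arms is built in. The text does not support that. The rule covers any parent, and naming the coach says who reports, not when the rule applies. Under Masking of Assessment Staff, coaches also run assessments, home visits and adverse event collection for families outside their own caseload. UC families are met every six months, and a coach or assessor who learns of an event must act on it. The hospital-stay, medical-care and medication items could bring some pregnancies to light, deliveries especially, and staff must follow up endorsed items. Zero detection in UC is therefore a limiting case, not an expectation.

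A reader might also infer that removed parents drop out of the intention-to-treat comparison. They do not: under the strategy carried over from the child they are imputed. What is lost is observed data.

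The direction is not guaranteed either. It depends on detection being higher in FBT. Treatment arm is not among the listed imputation variables, which would pull imputed FBT values toward the pooled relationship and dilute a real effect. Working the other way, those imputations may draw on on-treatment measurements although treatment was stopped. Neither effect is in the figures above.

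Other mitigations are real but partial. Pregnancy or a plan for it excludes at entry (Table 3), and a participating parent may be a father or guardian, so the rate should be low: q = 4% would mean 0.04 × 264 ≈ 11 UC parents. Participant Withdrawal or Termination lets the oversight bodies withdraw from analyses, in either arm, participants whose condition would distort the data, but that is discretionary. The planned outlier and no-imputation sensitivity analyses help somewhat. None of these supplies a pregnancy question or a pre-stated rule.

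**Conclusion.** The point holds as a gap in the data rules for a secondary aim. The exclusion from data collection creates avoidable missing 24-month parent BMI in either arm, against the plan's own missing-data aims, and this does not depend on any assumed rate. On top of that, there is a risk, not a certainty, that pregnancies are found and parents removed more often in FBT, which would tilt the parent BMI comparison toward FBT.

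The size rests wholly on assumptions (q 0.5% to 4%, g 1 to 4 kg/m²). It is 0.005 to 0.16 kg/m² with full FBT and no UC removal, 0.0025 to 0.08 with half of UC cases removed, and zero with equal removal. At the working SE of 0.31, type I error stays between 0.050 and 0.058 except in the most extreme corner (0.081). The effect is probably small. The child primary outcome is not affected, because the child continues. This is a cheap improvement to the plan, not a threat to its main conclusion.

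**What to change.** These changes concern data handling only and take no position on treatment in pregnancy.

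1. **Adverse Event Reporting Procedures.** Change both the sentence limiting the family's continuation and the exclusion form, so that a parent who becomes pregnant stays in the scheduled height and weight assessments where she agrees. Changing the form alone would leave the continuation sentence still removing her.
2. **Questionnaire.** Add one parent item on pregnancy and delivery date at 6, 12, 18 and 24 months, asked identically in both arms. Because dates are recorded, the order of weighing and questionnaire need not change.
3. **Analysis of Secondary Aim 1.** State one rule for both arms: a parent BMI measured during pregnancy, or within a fixed period after delivery, is set to missing and imputed, and later BMI is used as measured. Fix the length of that period before unblinding. Report pregnancies and removals by arm, and add a sensitivity analysis using parent BMI as measured.

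The cost is one questionnaire item, two wording changes in the protocol and a short addition to the analysis plan. The downside is that a few parent BMI values become imputed, now under the same rule in both arms.

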Families will be recruited from pediatric practices in our Practice-based Research Networks (PBRNs) in several ways. Each practice will have children who meet age, height, and weight criteria flagged in their charts, and we will use multiple approaches to recruit families. First, we will establish a ResearchMatch approach to recruiting in each PBRN. ResearchMatch, an online recruitment tool, will accrue families in one of two ways. At intake for a well- or sick-child visit, forms designed to acquaint families with the study will be introduced by PLAN coaches, and families can sign up for additional information about this study. Their information will be entered into a database by the PLAN coaches, and they will be contacted if they meet criteria. In addition, we will set up a website that they will be directed to in a flyer, and they can sign up to participate from the website. Since the pediatrician generally will not have information on parental health, this will need to be collected prior to deciding study eligibility, and the family database will assist in this endeavor by including information about all family members after a phone screen is conducted by the PLAN coaches with the participating parent. Second, PBRN practices post study advertisement at offices for interested families to visit the study website to complete questionnaires to ensure they meet eligibility criteria. If the families meet eligibility criteria, a PLAN coach will follow up with the families to schedule their first appointment at their earliest convenience. At this appointment, the PLAN coach will confirm the families' interest to participate and eligibility prior to participation. Third, Plan coaches will meet with families during well-child visits to introduce the study, assess their interest, and explain next steps. Each of these methods in collecting their information regarding interest and eligibility will be preceded by getting their verbal consent over the phone or a check box indicated on the web pages.

During recruitment, PLAN coaches will explain that there is a 50/50 possibility of getting one treatment over the other treatment. This will be like a flip of the coin and no one can just pick one treatment or the other. This study is testing if the FBT is as good as the care provided by their doctors normally given or better. Randomization will occur after the first appointment.

Inclusion Criteria

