Adverse event questionnaires and reporting forms are included in Appendix D of the study protocol. Once a site's research staff becomes aware of an adverse event's occurrence, that staff (i.e., PLAN coach or assessor) will consult with the clinical site PI or project coordinator to complete the appropriate event form and notify the SMC. Adverse event questionnaires will only be administered after assessment measurement by blinded measurement staff, who will correspondingly complete an adverse event log (10.12.20; *DSMB approval, 12.16.2020*). The SMC will then evaluate the severity of the event and determine the necessity for immediate action on behalf of the study group. If immediate action is necessary, the SMC will consult with the Steering Committee to recommend a course of action (e.g., discontinuation of treatment, referral to higher level care). If immediate action is not necessary, the event will be documented in the study database and discussed at the next scheduled DSMB meeting. Additionally, the DCC will prepare monthly reports that summarize adverse events and assess whether there is evidence of a between group difference in AE and SAE rates.

All adverse events and study withdrawals, together with a detailed explanation of the event and withdrawal, will be forwarded to the DCC and the DSMB. In addition, at its regular meeting, the DSMB will summarize all adverse events of any severity, to be forwarded to the IRB via the designated PI. All serious adverse events will be immediately recorded by the clinical site PI and reported to the IRB and DCC, via the designated PI; information (i.e., event, actions, and implications for study) will then be distributed to the other clinical sites. Any SAEs and AEs that are judged to be possibly or probably related to participation in the study and/or change their assessment of risk of participation will be immediately reported to the DSMB. The remaining SAE/AEs will be sent to the DSMB with the 6 month reports (***DSMB approved protocol addenda, 3.18.19***). If any participant appears to be in crisis but the event is not classified as an SAE, appropriate action will be taken based on established suicide and crisis protocols, and any adverse event will be reported promptly to the DSMB and IRB.

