Non-fatal, non-life-threatening unexpected, suspected serious adverse event	Within 15 calendar days of initial receipt of information	Contact PI	
 • IRB of Record • NHLBI • SMC • DCC • All PIs and Co-Is
		Clinical Site PIs	
 • Internal IRBs
Unanticipated problem that is not an SAE	Within 14 days of the investigator becoming aware of the problem	Contact PI	
 • IRB of Record • NHLBI • SMC • DCC • All PIs and Co-Is
		Clinical Site PIs	
 • Internal IRBs
All unanticipated problems	Within 30 days of the IRB's receipt of the report of the UP from the investigator.	IRB	
 • OHRP
		Contact PI	
 • IRB of Record
		Clinical Site PIs	
 • Internal IRBs
All non-serious AEs that are not UPs	Documented in study database and reported annually	Contact PI	
 • IRB of Record
		Clinical Site PIs	
 • Internal IRBs

Study Halting Rules for Participant Safety

There are few risks to family-based behavioral interventions. The intervention focuses on improving child and parent health behaviors through behavioral strategies and improved parenting and parent/child relations. The main risks are development of disordered eating or psychopathology and risks due to a sedentary person beginning to exercise. We will be carefully monitoring participants for excess weight loss, psychopathology, and activity-induced injuries. Although we expect that there will be very few serious adverse events, we will employ the following stopping guideline based on the number of SAEs in the intervention group. The guideline is summarized in **Table 11**, which provides data for maximum acceptable SAE rates of 2%, 4%, 6%, 8%, and 10% and for observed numbers of SAEs of 2, 3, 4, and 5. **Table 11** is calculated using 1-sided 95% binomial confidence intervals and can be interpreted as presenting the maximum total sample size N that is required in order to conclude that the toxicity level of the intervention may be excessive for a given number of

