observed SAEs and a given defined acceptable SAE rate. For example, suppose we define 2% as the maximum acceptable SAE rate. Then **Table 11** indicates that if the third SAE occurs in fewer than 41 intervention group subjects, then the guideline will have been exceeded because the SAE rate is greater than the acceptable 2% value with 95% certainty.

TABLE 11. MAXIMUM ACCEPTABLE SAE RATES

Number of Observed SAEs	Maximum Acceptable SAE Rate				
	2%	4%	6%	8%	10%
2	18	9	6	4	3
3	41	21	14	10	8
4	69	34	23	17	14
5	99	50	33	25	20

Several points about the above discussion are worth mentioning. First, we have used the term “guideline” instead of “rule” because we view the decision making process as one in which the guideline triggers a multifaceted discussion with the DSMB of whether the study should be stopped or modified because of the observed SAE rate. We do not view reaching the stopping boundary as a rule that should automatically lead to the termination of the study. Second, the rule will be applied both to parents and children separately. Third, we propose setting 2% as the maximum acceptable SAE rate because of the low anticipated SAE rate in this study.

At each DSMB meeting, recruitment and retention data will be presented to the DSMB. If recruitment is less than 90% of the target or if retention is less than 80% among randomized subjects, study investigators will present proposals for improvements in each of these two domains. Note that we use an 80% figure for retention because the original power computations had assumed a 20% dropout rate. Thus, an 80% retention rate is not an indication of reduced statistical power. If under performance by these definitions in either of these domains is present, the DCC will perform conditional power computations based on various scenarios regarding the degree of improvement that can be anticipated in recruitment and/or retention. As was the case in our original power computations, we will adopt the conservative approach of assuming that study dropouts provide no data. We propose that early termination be considered if the conditional power under the recruitment/retention scenarios the DSMB views as most realistic is less than 50%. Any final decision about recommending early termination will consider factors such as the impact of early stopping on information about secondary endpoints and covariate effects. It will also consider the adequacy of the measures that are proposed to increase recruitment and retention.

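### Does the SAE stopping guideline in Table 11 run out after the fifth event, well before each FBT group is fully enrolled?

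*Combined protocol and SAP*

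**What the plan says.** The section on study halting rules sets up a stopping guideline based on SAEs in the intervention group and says Table 11 summarises it. The table covers maximum acceptable rates of 2, 4, 6, 8 and 10% "and for observed numbers of SAEs of 2, 3, 4, and 5". It "is calculated using 1-sided 95% binomial confidence intervals and can be interpreted as presenting the maximum total sample size N" at which a given SAE count supports the conclusion that the rate may be too high.

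The worked example, for a 2% limit, says that "if the third SAE occurs in fewer than 41 intervention group subjects, then the guideline will have been exceeded". The text then proposes 2% as the working limit, because few SAEs are anticipated, and adds that "the rule will be applied both to parents and children separately". The 2% column reads 18, 41, 69 and 99 for the 2nd to 5th SAE.

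On the status of the boundary, the section says: "We do not view reaching the stopping boundary as a rule that should automatically lead to the termination of the study". Crossing it prompts a discussion with the DSMB.

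**The concern.** The Study Summary gives 528 families, and the Recruitment section tells families that "there is a 50/50 possibility of getting one treatment over the other treatment". Each monitored FBT group, children and parents separately, should therefore reach about 264. The last printed boundary at 2% is 99, so 165 of the 264 subjects (62.5%) lie beyond it. A 6th SAE is not remote if the true rate sits at the limit, and no row is printed for it.

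Two further points add to the unease. N is described as a total sample size in one sentence and as intervention group subjects in the next. Neither says whether this means subjects randomised so far or subjects whose follow-up is complete, which matters when entry is staggered and participation lasts two years. Also, fewer than 41 in the example excludes 41, while the definition of the entries makes 41 the largest qualifying N.

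Table 11 is the only numerical SAE threshold in the documents. If it stopped working after five events, a rate above the plan's own limit could build up without a numerical prompt.

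**Working it through.** **Inputs.** Printed rows, method, 2% limit and separate application: Study Halting Rules. 528 families: Study Summary. 50/50 allocation: Recruitment. Derived group size: 528 / 2 = 264.

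**Step 1: reproduce Table 11.** For SAE count k and limit p, take the largest N with P(X ≥ k | N, p) ≤ 0.05, X binomial. This is the same as asking that the one-sided 95% lower limit be at or above p. All 20 cells reproduce. For the 2% column:

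| k | N | P at N | P at N + 1 |
|---|---|---|---|
| 2 | 18 | 0.0495 | 0.0546 |
| 3 | 41 | 0.0486 | 0.0515 |
| 4 | 69 | 0.0497 | 0.0519 |
| 5 | 99 | 0.0491 | 0.0508 |

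The entries are inclusive maxima, so N = 41 itself meets the criterion. That is the one-subject mismatch with the worked example.

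**Step 2: carry the same formula on.** At 2% it gives 131, 165, 200, 236 and 273 for the 6th to 10th SAE. The 6th to 9th boundaries fall inside 264. At N = 264 the criterion is first met at 10 SAEs (P = 0.041, lower limit 2.07%); 9 do not meet it (P = 0.086, lower limit 1.79%).

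**Step 3: how likely is a 6th SAE?** P(X ≥ 6 | 264, p) is 0.434 at p = 2% and 0.954 at 4%. It is 0.051 at 1% and 0.002 at 0.5%. The documents give no expected rate, so all four are assumptions. They do say that very few SAEs are expected, and 2% is a ceiling.

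**Step 4: what the missing rows would cost if only printed rows were used.** Assume at most one SAE per subject, N = follow-up completed, and a check after each subject up to 264 (exact recursion):

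| True rate | Printed rows only | Same criterion continued |
|---|---|---|
| 1% | 2.2% | 2.3% |
| 2% | 11% | 16% |
| 3% | 27% | 45% |
| 4% | 47% | 75% |
| 5% | 64% | 91% |

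Reading the printed entries strictly (fewer than) moves the 4% figure only from 46.6% to 45.4%.

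**Step 5: N as subjects randomised to date.** The accrual milestones show 84 families in each quarter of 2018, so 84 / 3 / 2 = 14 FBT subjects a month. The documents give no SAE timing, so events were simulated uniformly over an assumed window after entry (40,000 trials). At a true 4%, the chance of a prompt is 24% (printed) against 67% (continued) for a 3-month window, and 0.06% against 61% for a 24-month window. The second contrast looks dramatic, but about 60 of those 61 points come from the 10th or a later SAE. Its boundary (273) exceeds the group size, so that crossing means only that ten SAEs have occurred. The near-zero printed figure arises because enrolment runs ahead of events, which is a matter of how N is counted.

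**The case for a change.** The best argument for amending the plan is that a pre-specified safety threshold should not depend on inference. The text never commits to using the formula past the fifth SAE, and extending the formula does not settle how N is counted. That choice matters even with the column continued: at a true 4% the chance of a prompt is about 60–68% with N as randomised to date (over the accrual rates and timing windows tried) and 75% with N as follow-up completed. The clarification would also be cheap.

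Part of this stands. The two silences are real, and so is the mismatch over 41. But the silence about continuation is weak evidence of a lapse. The method is stated for whatever number of SAEs is observed, and the table also prints four rates that were not adopted, so it reads as an illustrative grid. As for N, neither choice dominates. Counting randomised subjects gives fewer prompts at a true 2% (4–8% against 16%) and also fewer at 4%. The DCC and DSMB can settle that when the first report is prepared.

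The mention of "risks due to a sedentary person beginning to exercise" might suggest early events, but it does not establish SAE timing. Table 8 lists the physical-activity events as adverse events, and an SAE requires death, threat to life, hospitalisation or lasting disability.

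**Conclusion.** No change is needed. Table 11 is arithmetically right, its criterion is stated, and a statistician at the coordinating centre would continue it past the fifth SAE without instruction. The largest well-defined contrast at a true 4% (47% against 75%) rests on three assumptions: the guideline lapses after the printed rows, N is follow-up completed, and the true rate is twice the limit. The documents support none of these. At an assumed 1% the two versions barely differ (2.2% against 2.3%).

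The practical stake is also small. The boundary opens a discussion and dictates no action. Alongside it the DSMB reviews data every six months (Safety Oversight). SAEs judged possibly or probably related go to the DSMB at once, and the DCC's monthly reports "assess whether there is evidence of a between group difference in AE and SAE rates" (Adverse Event Reporting Procedures). Severe events that may be study related reach the DSMB chair within 72 hours (Summary Reports). A tenth SAE in a group would be in front of the DSMB whether or not a row had been printed for it.

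What remains is a gap that analysts would fill sensibly, a counting choice with a fair trade-off either way, and a one-subject slip in the worked example beside a correct table.
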